In PsA but also in chronic arthritis in general, integrating imaging in clinical practice is the challenge of the near future and for clinical feasibility it is essential to identify an US composite score that could explore all the domains of the disease, especially in the polymorphic PsA.

In 2012 *Gutierrez et al.* developed a Power Doppler composite score focused on joints, tendons, entheses, skin and nails and the final target was to define the overall disease activity.⁽¹³⁾ The German US7-joints score is another viable tool for examining patients with chronic arthritis in daily practice. Developed mainly for RA, it was also effective for monitoring therapy in peripheral PsA.⁽¹⁴⁾ More recently *Ficjan et al* developed two new US composite scores (PsASon-13 and PsASon-22), derived from a total ultrasound score (68 joints/14 entheses) in order to have a high sensitivity to detect PsA features and a good feasibility in clinical practice.⁽¹⁵⁾ However no simplified scores are fully validated in terms of content, construct and criterion so far. For this reason extensive US evaluations are needed to assess PsA in clinical practice and research.

AIM

The aim of this study is to identify clinical and US predictors of achieving MDA in PsA patients with active peripheral arthritis starting a new course of therapy.

Identifying prognostic factors of achieving remission or low disease activity will allow a better selection of patients with poorer outcome and a following improvement of the therapeutic strategies. Furthermore the possibility that US could be an added prognostic value makes this study a clear example of integration between the clinic and US. This study will respond to the need of tailoring treatment that would allow clinicians to practice a more effective and personalized medicine, optimizing the outcomes of patients with PsA as well as the treatments management.

STUDY OBJECTIVES

PRIMARY OBJECTIVE

In clinically diagnosed PsA with clinically active joint disease starting a new course of therapy, to evaluate the additional value of US-score (US-score PsA-SIR) over clinical examination in detecting patients achieving MDA at 6 months.

SECONDARY OBJECTIVES

In clinically diagnosed PsA with clinically active joint disease starting a new course of therapy:

- to evaluate the additional value of US over clinical examination in detecting patients:
 - achieving MDA at 12 months (including sustained)

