A total of 30 static images per US-lesion type (synovitis, enthesitis, tenosynovitis, erosion, bony apposition) with 50% of presence of lesions will be submitted to scoring through an on-line electronic platform. A reference atlas will be provided to the investigators before the exercise. A second exercise could be offered to investigators who did not achieve a minimum level of kappa after further training at one of the Centres of the PIs.

SCREENING VISIT

The aim of this visit is to identify a patient who might be suitable for inclusion in the study.

- Consent: Inform the patient about the nature and objectives of the study and obtain his/her written informed consent;
- Check inclusion/exclusion criteria;
- Check cumulatively CASPAR criteria since the onset of PsA;
- Assign patient number (PN) in sequential order, if the patient is suitable for the inclusion in the study.

BASELINE VISIT

The aim of this visit is to confirm that the patient is appropriate for inclusion in the study, determine disease activity state, undertake a complete high resolution ultrasound assessment and X-ray of hands and feet. If a X-ray has been already done within the 6 months before the study entry is not requested to perform a further scanning.

- Record in Case Report Form:
 1. demographic and life-style variables (*smoking, alcohol consumption, BMI*);
 2. drug history (*including past adverse events*);
 3. typical comorbidities associated to PsA (*obesity, diabetes, hypertension, metabolic syndrome non-alcoholic fatty liver disease, IBD, uveitis, anxiety/depression*) and other comorbidities (*e.g. neoplasms, cardiovascular disease, Charlson comorbidity index*);
 4. onset of symptoms and disease duration;
 5. define clinical subset of PsA;
 6. CPR (mg/dl), ESR;
 7. RF, ACPA and HLA B27 (if available);
 8. treatment to be started;
- Procedures for psoriatic arthritis:
 1. Swollen (68) and Tender (66) Joints Count;
 2. Enthesal assessment;
 3. Tender Dactylitis Count;

- Procedures for psoriasis:
 1. Body Surface Area (BSA);
- Questionnaires:
 1. Physician completes VAS Physician global assessment of disease activity (joint and skin) 0-100;
 2. Patients completes pain VAS (0-100), global VAS (0-100), HAQ, BASDAI, PSAID12;
- US assessment:
 1. US-score PsA-SIR;
- X-ray assessment of hands and feet:
 1. Posterior-anterior radiographic assessments of hands and feet (electronic format)

3RD MONTH VISIT

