 1. Physician completes VAS Physician global assessment of disease activity (joint and skin) 0-100;
 2. Patients completes pain VAS (0-100), global VAS (0-100), HAQ, PsAID12
- US assessment:
 1. US-score PsA-SIR
- X-ray assessment of hands and feet:
 1. Posterior-anterior radiographic assessments of hands and feet (electronic format)

CLINICAL ASSESSMENT

The demographic variables describing the patients will be age, sex, ethnic group, family history, body weight, height and smoking. On enrolment in the study, a detailed medical history will be recorded mostly focusing on PsA (onset of symptoms, date of diagnosis), related treatment (current and previous medication, reason for withdrawal) and associated comorbidities (e.g. SpA spectrum comorbidities). To assess comorbidities, disease specific recommendations will be followed.⁽¹⁷⁾

To increase feasibility and reliability metabolic syndrome will be defined as follows: 1) BMI > 30 kg/m²; 2) a diagnosis of type 2 diabetes mellitus and 3) a diagnosis of hypertension.⁽¹⁸⁾

Each patient considered eligible for the study will be classified according to clinical subset(s) of PsA:

- 1- Monoarticular or asymmetric oligoarthritis with or without dactylitis.
- 2- Symmetric polyarthritis similar to rheumatoid arthritis.
- 3- Classic psoriatic arthritis confined to distal interphalangeal joints of hands and feet.
- 4- Spondylitis with or without peripheral joint involvement
- 5- Arthritis mutilans

CLINICAL EFFICACY

Clinical response and clinical remission will be based on the following variables:

- 1- Minimal Disease Activity (MDA)
- 2- Disease Activity for Psoriatic Arthritis (DAPSA)
- 3- ACR response score

The sonographer should be blinded to minimize bias associated with disease activity score evaluation. In addition, every effort should be made to ensure that the same member of staff performs the disease activity assessment on successive visits for a given patient.

The MDA calculation will be based on the evaluation of 7 variables:

- a) 68 tender joints count (≤ 1)
- b) 66 swollen joint count (≤ 1)
- c) BSA ≤ 3
- d) Patient pain VAS (≤ 15 mm);
- e) Patient global disease activity VAS (≤ 20 mm);
- f) HAQ (≤ 0.5);
- g) Leeds Enthesitis Index (LEI) tender enthesal points (≤ 1)

Patients will be classified as having MDA if they meet 5 out of these 7 criteria (value in brackets).

The DAPSA calculation is based on the evaluation of 5 variables:

- a) 68 tender joints count
- b) 66 swollen joint count

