- c) Patient's pain (VAS)
- d) Patient's global disease activity assessment (VAS)
- e) C-reactive protein

As a result the DAPSA index gives a value with:

- >28 indicating high disease activity
- 14-28 indicating moderate disease activity
- 4-13 indicating low disease activity
- ≤ 4 indicating complete remission

Using DAPSA the clinical response can be defined:

- Minor : 50% DAPSA change from baseline
- Moderate: 75% DAPSA change from baseline
- Major : 85% DAPSA change from baseline

The ACR20 response criteria require $\geq 20\%$ [ACR50 $\geq 50\%$ or ACR70 $\geq 70\%$] improvement in both the TJC and SJC, as well as a 20% improvement in 3 of the following 5 items:

1. patient global assessments of disease activity (VAS),
2. patient reported pain score (VAS),
3. physician global assessment (VAS),
4. Health Assessment Questionnaire (HAQ),
5. either ESR or CRP.

METHODS OF ASSESSMENT

Patient's assessment will be performed according to the core set of domains for PsA proposed by the Group for Research and Assessment of Psoriasis and Psoriatic Arthritis (GRAPPA) and Outcome Measures in Rheumatology (OMERACT).^(19,20)

Assessment of **Peripheral Joint Activity** will be performed using the 68 tender joint count and the 66 swollen joint count. Positive joints will be recorded and the total number of tender and swollen joints will be calculated. As it may be difficult to distinguish proximal inter-phalangeal (PIP) from distal inter-phalangeal (DIP) joint inflammation in the toes, if either the PIP or DIP of the toe is involved it should be marked as a PIP.

Patient global assessment (PtGA) and **Physician global assessment (PGA)** will be assessed by Visual Analogues Scores (VAS) as it is a reliable tool related to joint and skin disease activity. **VAS PGA of disease activity (0-100)**

Physicians will take into account both the severity of joint and skin disease when making the assessment on the scale. The left end corresponds to “completely inactive” and the right end to “highly active”.

- **VAS PtGA of disease activity (0-100)**

The patients are instructed to rate their overall state of disease (joint and skin) on the scale. Recall period: past week. The left end corresponds to “completely inactive” and the right end to “highly active”. The patients will mark their own assessment on the scales in the case report forms by themselves by placing a single vertical line through the bar.

- **VAS PtGA of pain (0-100)**

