US IMAGING						
US-score PsA-SIR		X		X	X	X
CR IMAGING						
X ray (hands-feet)		X			X	X
ADVERSE EVENTS			X	X	X	X

STATISTICAL ANALYSIS PLAN

VARIABLES: OUTCOME MEASURES

PRIMARY:

- MDA at 6 months

SECONDARY

- MDA at 12 months, sustained MDA at 6 AND 12 months
- DAPSA <3.3 at 6 months, 12 months, 6 AND 12 months
- Δ mSvH 0-12 and 0-24 months
- Δ HAQ 0-12 and 0-24 months
- Δ PSAID 0-12 and 0-24 months
- US-score PsA-SIR damage subscore at 0-6-12 months

US PREDICTORS

- US-score PsA-SIR
- US-score PsA-SIR inflammation subscore
- US-score PsA-SIR damage subscore

CLINICAL PREDICTORS

Based on the relevant literature clinical variables to be considered in the model include:

- Demographic and environmental factors:
 - Age
 - Gender
 - Smoking
 - BMI
- Clinical factors:
 - subset of PsA
 - time from symptoms onset to diagnosis
 - disease duration
 - disease activity (DAPSA and BASDAI)
 - HAQ score
 - tender joints / pain
 - comorbidities (FM, MetS)
- Serological factors:
 - Acute phase reactants
- Therapy factors:
 - Treatment (NSAIDs, steroids, DMARDs)

DESCRIPTIVE ANALYSES

Descriptive data will be provided for all outcomes according to data type; number of patients (N), mean, standard deviation (for interval data), median 25% and 75% quartiles (for ordinal data). Frequency (absolute and relative) distributions will be provided for categorical data. Two-sided p-values will be presented throughout.

PRIMARY ENDPOINT ANALYSIS

Prediction of 6 months MDA will use multivariate adjusted logistic models. A baseline model will include all the clinical variables. US predictors will be added as covariates to the clinical variables, assuming an additive model. The derived β coefficients were used to calculate prognostic indices, thereby creating weighted prediction models.

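### Baseline skin extent (BSA) is an item of the primary outcome and is already collected, but the clinical model against which ultrasound is judged has no skin term; the likely effect is modest and the repair is cheap.

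*Combined protocol and SAP*

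**What the plan says.** The Statistical Analysis Plan names "MDA at 6 months" as the primary outcome. The protocol's Clinical Efficacy section lists seven MDA items, the third being BSA ≤ 3, and gives the rule: "Patients will be classified as having MDA if they meet 5 out of these 7 criteria (value in brackets").

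The Baseline Visit section lists "Body Surface Area (BSA") under the psoriasis procedures, and the visit schedule marks it at baseline and at months 3, 6, 12 and 24.

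The primary objective is the added value of the US score "over clinical examination in detecting patients achieving MDA at 6 months". The Clinical Predictors list opens with "Based on the relevant literature clinical variables to be considered in the model include" and names age, gender, smoking, BMI, PsA subset, delay from symptoms to diagnosis, disease duration, DAPSA, BASDAI, HAQ, tender joints/pain, fibromyalgia, metabolic syndrome, acute phase reactants and treatment. Under Primary Endpoint Analysis, "A baseline model will include all the clinical variables", and "US predictors will be added as covariates to the clinical variables, assuming an additive model".

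**The concern.** The primary question is a comparison of two models, so the estimated worth of US depends on how complete the clinical model is. Five of the seven MDA items have their baseline value represented: tender joints, pain and HAQ by name, and swollen joints and patient global through DAPSA. BSA and the Leeds Enthesitis Index (LEI) do not.

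The baseline value of BSA should matter for the outcome. Eligibility requires an active joint and absence of MDA but sets no skin condition, so patients may enter on either side of the threshold. A patient who starts above 3 must either fall to 3 or below or meet 5 of the other 6 items; one who starts at or below 3 usually has an item in hand. No term in either model carries this difference directly: DAPSA has no skin item, and the PsA-SIR score sums joint, tendon, entheseal and bursal lesions.

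Two consequences are possible. Unexplained variation in MDA can slightly dilute the US coefficient. And if BSA is still related to the US score once the listed variables are held fixed, part of the skin effect will be attributed to US, or masked by it.

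**Working it through.** **1. The plan's own figures.** Sample Size gives 250 patients, MDA probability 0.4 and 10 predictors: 250 × 0.4 = 100 events, and 100 / 10 = 10 events per predictor.

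It also gives 90% power for a false-positive rate of 0.4 falling to 0.2 at a true-positive rate of 0.7, with 150 + 100 patients. Assuming an equal-variance binormal ROC curve (the shape is not stated):
- The null curve at FPR 0.2 has TPR = Φ(0.778 − 0.842) = 0.475, against 0.70 under the alternative.
- The variance of the empirical ROC point is 0.21/150 + 1.242² × 0.16/100 = 0.00387, so SE = 0.0622, or 0.0622/0.21 = 0.296 on the logit scale.
- Power = Φ((0.847 + 0.102)/0.296 − 1.960) = 89.3%, close to the stated 90%. Other variants (raw scale, one-sided, FPR at fixed TPR, one-sample binomial) gave 88% to 99.5%.

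No covariate enters this calculation, so adding or omitting BSA leaves the stated sample size and power unchanged.

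**2. How often the BSA item decides MDA.** It is decisive only when exactly 4 of the other 6 items are met. With MDA set to 40%, that is about 30% of patients if the items are independent, and about 10 to 20% if they share a common factor (item correlation 0.3 to 0.7). All of these correlations are assumptions.

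**3. Simulation of the item count** (n = 250, 600 replicates, 40% MDA; assumed 30–50% with baseline BSA > 3, and month-6 BSA ≤ 3 in 95% of those starting low and 30–70% of the rest).
- With US unrelated to BSA, MDA differed by 4 to 12 percentage points between low and high baseline BSA. Power for the US term hardly changed.
- Adding BSA raised the clinical AUC by up to about 0.01, or up to about 0.02 when US and BSA were correlated.
- Correlation −0.3: power for US was 85–91% without BSA and 91–93% with it.
- Correlation +0.3: 95–97% without BSA and 91–93% with it, so the US signal is overstated.
- Useless US score: rejection up to about 9% without BSA, about 5% with it.

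**4. Separate logistic simulation** (BSA effect −0.2, −0.4 or −0.7 log-odds per SD; BSA–US correlation 0 to 0.3 given the clinical score).

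| Setting | Without BSA | With BSA |
|---|---|---|
| True US coefficient −0.40, correlation 0 | −0.39 to −0.37 (attenuated about 1–9%) | about −0.40 |
| True US coefficient 0, correlation 0.1–0.3: false AUC gain | at most about 0.006 | about 0 |
| True US coefficient −0.40, correlation 0.1–0.3: AUC gain credited to US | 0.027–0.048 | 0.015–0.024 |

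The 4 to 12 point gap in step 3 corresponds, with 40% above BSA 3 (SD = √0.24 = 0.49), to about 0.04/0.24 × 0.49 = 0.08 up to 0.12/0.24 × 0.49 = 0.25 log-odds per SD in absolute size. The −0.2 setting is therefore the relevant one. There, for a real US effect, the credited AUC gain is 0.027–0.032 without BSA against 0.021–0.024 with it; for a useless score the false gain is at most 0.0006.

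**5. Degrees of freedom.** The list has 15 named variables (tender joints/pain counted as one). With subset at 5 levels (4 df) and treatment at 3 (2 df), that is 13 + 4 + 2 = 19 df. One US term makes 20, and BSA makes 21. At 100 events, events per df go from 100/20 = 5.0 to 100/21 = 4.8.

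**The case against.** - *Skin is already in the model.* The patient global is a component of DAPSA, and "The patients are instructed to rate their overall state of disease (joint and skin) on the scale". That is true but indirect: it is one mixed rating among five components and does not show which side of BSA 3 a patient is on.
- *The list is not closed.* Its opening wording leaves room for more variables. But the model takes all the clinical variables and nothing adds BSA; adding it after the data are seen would be a post hoc choice in the primary comparison.
- *Treatment is already adjusted for.* So treatment choice is at least partly blocked as a route from skin to US. This stands, and it makes a large residual correlation less likely.
- *The plan's own measures barely move.* US is to be judged by AUC, NRI and IDI; the rejection rates above belong to a test of the US coefficient that the plan does not name. This stands, and it is why the point is modest.
- *The model is already too large.* It is, by about 9 df against the budget of 10 (19 − 10). That argues for removing overlap, not for leaving an outcome item unrepresented.

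Two stronger readings are tempting. A reader might apply the linear-model variance formula with a correlation of 0.5 between BSA and MDA: Φ(3.242/√0.75 − 1.960) = 96.3%, a gain of 6.3 points. That formula is for a continuous outcome, not a logistic or ROC analysis, and a 4 to 12 point MDA gap implies a correlation of only about 0.04 to 0.12, for which the same formula gives at most 90.4%. A reader might also infer serious false-positive inflation: the logistic simulation reached 14% and 28% at BSA effects of −0.4 and −0.7. Those effects imply MDA gaps of about 19 and 32 points, well beyond what the item-count simulation produces.

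**Conclusion.** The point holds as a modest weakness of the primary comparison. It is certain from the text that BSA is an MDA item, that it is measured at baseline, and that neither model has a direct skin term. The comparator for US therefore omits a bedside baseline value of the outcome's own items.

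The size is not certain. With BSA unrelated to US, the loss is a slight attenuation and almost no power. With a residual correlation of ±0.3, the US increment can err in either direction: rejection of a true null up to about 9% instead of 5%, a false AUC gain of at most about 0.006, or 1 to 6.5 points of power lost. The correlation, its sign and the BSA effect are all assumptions. The documents do not show that skin status will be credited to US, only that the plan does not prevent it. Nor do they support a claim that the sample size or the stated power is wrong on this account.

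**What to change.** In the Clinical Predictors list, add baseline BSA as one prespecified term, coded either at the MDA threshold (≤ 3 versus > 3) or as log(BSA + 1), with the choice fixed in advance. Keep it in both the clinical and the clinical-plus-US models for MDA at 6 months, MDA at 12 months and sustained MDA. Baseline LEI, the other MDA item absent from the list, can be treated the same way; it also overlaps with US, which scores entheses.

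The change needs a line of SAP text and no new data or visits. The cost is one degree of freedom per term in a list already above the 10-predictor budget. It can be offset by not entering separately what DAPSA already contains (tender joints, pain, CRP). On the count above, dropping the tender joints/pain and acute phase reactant terms and adding BSA and LEI gives 20 − 2 + 2 = 20 df, the same as now. ESR is not part of DAPSA, so dropping the acute phase term would lose it. The excess over the budget remains and needs its own decision.

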- results in persistent or significant disability/incapacity
- constitutes a congenital anomaly/birth defect
- requires inpatient hospitalization or prolongation of existing hospitalization.

ULTRASONOGRAPHIC ASSESSMENT

Sonographic evaluations will be performed by expert ultrasonographers on the same day of clinical assessment and must invariably be performed after the clinical decision to change the patient's treatment. Furthermore, results of ultrasonographic evaluation should not be taken into account for the choice of treatment.

Grey scale (GS) and power Doppler (PD) sonography will be performed in 44 joints, 36 tendons, 12 entheses and 2 bursae (US-score-PsA-SIR) using a high standard US machine and multi-frequency linear transducers (high frequency probe at least 14 Mhz).

In the absence of a definition of the ultrasound **bone proliferation** in PsA, we propose to use the OMERACT definition of osteophyte (formation of excess bone at the joint margins).^(21, 22) Score dichotomous: 0 – Absent, 1 – Present.

In accordance with Terslev L. et al⁽²³⁾ the elementary lesions considered to evaluate **enthesitis** were: hypoechogenicity (indicate increased thickness with blurring of the tendon margins); increased thickness of tendon insertion; enthesophyte (the step up of the bony prominence at the end of the normal bone contour is marked with white arrowheads); calcifications; bone erosion at the enthesis; Doppler at enthesis <2 mm from the bone insertion. In addition to single elementary lesions, global definition of enthesitis will be recorded.

Erosions will be defined as an intra-articular discontinuity of the bone surface that is visible in 2 perpendicular planes.⁽²⁴⁾

Sonographically the two criteria for the definition of **bursitis** have been represented by: pathological effusion into the bursae (shown as an anechoic material) and hypertrophy of the synovial membrane (displayed as material into the bursae, which can appear hypoechoic, isoechoic or hyperechoic compared with subcutaneous fat). Bursitis may also be characterized by the presence of the Doppler signal within the synovial proliferation. For some bursae as the bag deep infrapatellar bursa and deep Achilles bursa minimum fluid distension, in the absence of synovial proliferation, are considered physiological.

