If in addition to an abnormal peritendinous (ie, intra-sheath) signal there was an abnormal intratendinous signal seen in two perpendicular planes (ie, excluding intratendinous small isolated signals that can correspond to normal feeding vessels detectable by US), then grades 1 and 2 would be increased by one point ⁽²⁸⁾.

Tendon damage can be defined on B-mode as internal and/or peripheral focal tendon defect (ie, absence of fibers) in the region enclosed by tendon sheath, seen in two perpendicular planes. The grade of tendon damage should be assessed in both longitudinal and transverse planes. ⁽²⁹⁾

The overall PsA-SIR US score will be calculated as the sum of the scores of every lesion at all sites (range 0-632).

The inflammatory PsA-SIR US subscore will be calculated as the sum of the scores of GS-sinovitis, PD-sinovitis, GS-tenosynovitis, PD-tenosynovitis, GS-peritenotitis, PD-pertitenonitis, enthesal hypoechogenicity, enthesal thickness, enthesal PD, GS-bursitis and PD-bursitis at all sites (range 0-470).

The damage PsA-SIR US subscore will be calculated as the sum of the scores of joint erosion, bony proliferation, tendon lesion, enthesophytes, enthesal calcifications, enthesal erosions, at all sites (range 0-162).

RADIOGRAPHIC ASSESSMENT

Posterior-anterior radiographic assessments of hands and feet will be scored at a subsequent time point by two radiologists centrally using the van der Heijde modification of the Sharp score. The scoring will be performed pairwise, blinded to the sequence of the films and to the clinical data. Mean of two investigators will be taken as the final score for X-ray assessments.

STUDY VISIT/SCHEDULE

Study Period:	Enrollment	Observation/Follow-up MONTHS				
Visit	Screening	Baseline	3	6	12	24
Informed Consent	X					
Inclusion/Exclusion Criteria	X					
Socio-demographic data		X				
Life-style questionnaire		X				
Medical History		X				
Information treatment		X	X	X	X	X
ARTICULAR ASSESSMENT						
Tender (68) and swollen (66) joint count		X	X	X	X	X
Entheseal assessment		X	X	X	X	X
Tender Dactylitis Count		X	X	X	X	X
SKIN ASSESSMENT						
Body Surface Area (BSA)		X	X	X	X	X
BLOOD TEST						
RF/ACPA/HLA-B27		X				
ESR/CRP		X		X	X	X
PATIENT GLOBAL AND PAIN ASSESSMENT						
Pain VAS		X	X	X	X	X
Global VAS		X	X	X	X	X
PHYSICIAN'S GLOBAL ASSESSMENT						
Physician's Global VAS		X		X	X	X
PATIENT SPINAL ASSESSMENT						
BASDAI		X				
PHYSICAL FUNCTION						
HAQ		X	X	X	X	X
HEALTH-RELATED QUALITY OF LIFE						
PsAID-12		X		X	X	X

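### Does the primary model fail because it names no ultrasound score, when the overall score is the sum of its two listed subscores?

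*Combined protocol and SAP*

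**What the plan says.** The Primary Objective is "to evaluate the additional value of US-score (US-score PsA-SIR) over clinical examination in detecting patients achieving MDA at 6 months". It concerns one named score. The Aim is wider: "The aim of this study is to identify clinical and US predictors of achieving MDA".

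Under US Predictors, the SAP lists three measures in this order: the overall score, the inflammation subscore and the damage subscore. The Primary Endpoint Analysis first fits a model with the clinical variables and then extends it: "US predictors will be added as covariates to the clinical variables, assuming an additive model". It continues: "The derived β coefficients were used to calculate prognostic indices, thereby creating weighted prediction models". Added value is judged by AUC, NRI, IDI and ROC curves. The Secondary Endpoint Analyses follow the primary approach.

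The Ultrasonographic Assessment section defines the scores. The total is given as "The overall PsA-SIR US score will be calculated as the sum of the scores of every lesion at all sites (range 0-632"). The inflammatory subscore sums its items "at all sites (range 0-470"), and the damage subscore sums its own "at all sites (range 0-162"). On the entheses the section adds: "In addition to single elementary lesions, global definition of enthesitis will be recorded".

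**The concern.** Read literally, the analysis sentence puts every listed US predictor into one model. If the total is the sum of the two subscores, that model has no unique coefficients. One term must go, and what remains is a two-term subscore model rather than the single-score model of the objective. Because the coefficients become weights in a prognostic index, the weight printed beside the overall score could then be that of a subscore.

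Read the other way, each score gets its own extended model. There are then three estimates of added value, and the analysis section does not say which one answers the primary question. The secondary endpoints would inherit the same doubt. At stake would be a primary result whose defining covariate was chosen after the data were seen.

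**Working it through.** **1. Is the total exactly the sum of the subscores?** The inputs are the ranges and lesion lists in the Ultrasonographic Assessment section.

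- Inflammatory maximum 470, damage maximum 162, stated total maximum 632.
- 470 + 162 = 632, so the stated total is reproduced with no remainder.
- The lists (11 inflammatory items, 6 damage items) do not overlap. The six elementary enthesis lesions split three and three between them.
- The global enthesitis definition is in neither list. If it were scored 0/1 at the 12 entheses (assumed coding) and counted in the total, the maximum would be 632 + 12 = 644. The stated range leaves no room for it.

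So T = I + D, where T is the total, I inflammation and D damage.

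**2. What happens if all three are entered?** The intercept plus T, I and D make four columns of rank 3, whatever the data. For any coefficients bI and bD:

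bI·I + bD·D = bD·T + (bI − bD)·I = bI·T + (bD − bI)·D

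The linear predictor is the same for every pair of scores. The fitted risks are therefore the same, and so are AUC, NRI and IDI. A check on 250 simulated patients (lesion distributions assumed) gave log-likelihood −152.938783 for I + D, for T + I and for T + D. T alone gave −155.380321. Only the labels on the coefficients depend on which term is dropped.

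**3. How far apart are the one-score and two-subscore models on the planned measures?** The documents give neither the correlation between the subscores nor their SDs, so a range was used. Inputs:

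- n = 300 × 0.8 = 240 and MDA 40%, from the Sample Size section;
- 10 clinical covariates, taken from its 10-predictor statement;
- clinical AUC 0.70 (assumed);
- no true US effect (assumed);
- subscore correlation −0.2 to 0.9 and SD ratio 1 to 5 (assumed), in five combinations of 2,000 replicates each.

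| Extended model | Mean apparent AUC gain | Mean IDI |
|---|---|---|
| Total only | 0.0029–0.0031 | 0.0039–0.0040 |
| Both subscores | 0.0059 | 0.0078 |
| Best of the three single scores | 0.0042–0.0058 | 0.0051–0.0071 |

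The Monte Carlo standard error of the AUC gain is at most 0.00015. Two subscores against the total: 0.0059 − 0.0031 = 0.0028 to 0.0059 − 0.0029 = 0.0030 in AUC, and 0.0078 − 0.0040 = 0.0038 to 0.0078 − 0.0039 = 0.0039 in IDI.

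**4. Does the plan already choose?** The Primary Objective gives the overall score by name, and the predictor list puts it first. The analysis section speaks of models in the plural. That fits separate models, although a clinical model plus one extended model would also be plural. No sentence calls for joint entry.

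**The case for a change.** The strongest case for a change is that a reader should not have to look in the objectives to learn the only new covariate of the primary model. The US Predictors list gives no order of importance, and the Aim of identifying US predictors invites all three scores. The Secondary Objectives speak of US in general, so for those endpoints the choice rests only on the statement that the primary approach is followed. A few sentences would close the gap at no cost in data.

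The choice can also matter when there is a real effect. The total weights one point of damage and one point of inflammation equally. At an assumed subscore correlation of 0.3 and SD ratio of 3 (inflammation to damage), it correlates (3 + 0.3)/√(9 + 1 + 1.8) = 0.96 with inflammation but (0.9 + 1)/√11.8 = 0.55 with damage. A signal carried by damage alone would be diluted.

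What stands is that the sentence is incomplete and that the models answer different questions. What does not stand is that the primary question is left open, since the objective settles it. The dilution is a property of the score the investigators chose, not a result of the gap. The worry about weights arises only under joint entry, and the dropped term would show in the output. A false-positive argument over three tests would need a success rule that the SAP does not state and correlations that the documents do not give. Whether the subscores are best examined in one secondary model or in separate ones is a matter of preference.

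**Conclusion.** The algebra is right: the three listed scores are linearly dependent, and the analysis sentence names none of them. It is still missing detail rather than a fault in the design. An analyst who reads the Primary Objective beside the SAP fits the overall US-score PsA-SIR as the US term, treats the subscores as further candidates, and carries the same choice to the secondary endpoints. If all three were entered by mistake, the dependence would be visible and the planned performance measures would not depend on which term was dropped.

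The largest effect of that mistake on the reported gain is about 0.003 in apparent AUC and 0.004 in IDI when US has no true effect, under the assumptions given above. With real and unequal subscore effects the models could differ more, but the objective still says which of them is primary. No change to the plan follows.
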